Effective Screening for Pain Study

NCT01816763

July 2018

Abstract

Objectives: The overall objective of our mixed method study is to evaluate a strategy to improve the quality and clinical usefulness of ‘the 5th Vital Sign’ in VA primary care. We will formatively evaluate experiences with and implementation of the *enhanced pain screening approaches* (patient self administered computer aided) including clinician perspectives on the use of pain screening to guide management. Our specific aims are to:

Aim 1. Characterize primary care team and Veteran patient perspectives on enhanced pain screening approaches compared with usual pain screening re., clinical usefulness and how to use skills, roles, and tasks of multidisciplinary clinicians and consultants to optimize pain care. Interviews and focus groups will inform development of the screening interface. **Aim 2.** Evaluate in a three-arm RCT the effects of enhanced pain screening approaches using the PEG (Arm 1), the ‘NRS pain now (Arm 2), compared with DVPRS (Arm 3) followed by usual clinician-assessed pain screening, on the detection of patient pain as well as feasibility, acceptability, and experiences with (e.g., pain missingness), patient-reported tablet-based pain assessment using quantitative patient screening outcomes, and interviews with patients, clinic, and facility staff **Research Plan:** At three sites (VA GLA, Minneapolis, and Portland) we will conduct interviews and focus groups with primary care staff about their experiences with pain screening and how to link screening to management in order to inform development of an integrated enhanced pain screening approach (using PEG and NRS now and DVPRS) on a touchscreen together with survey questions on risk for under-assessed or under-treated pain. The integrated protocol will be installed on a touchscreen tablet to use in a 3 arm RCT to evaluate the optimal approach to pain screening, along with an evaluation of the implementation experience.

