3.0 Objectives

The overall objective of our mixed method study is to evaluate a strategy to improve the quality and clinical usefulness of 'the 5th Vital Sign' in VA primary care. We will first develop a patient-self administered computer-aided pain assessment, then evaluate and refine the assessment using human-computer interaction laboratory usability testing. Next we will conduct a three site randomized controlled trial (RCT) to test a computer-based pain assessment protocol compared with usual pain screening. In the RCT we will evaluate three arms – one arm will use the PEG, a more sensitive screener including pain functional impairment, and a second arm will replicate the 'NRS now' allowing a direct comparison of patient-administered assessment vs. clinician assessed pain and a third arm will test the NRS at one week. All subjects will be screened with the '5th Vital Sign'. (allowing a three arm comparison of each of two computer based approaches vs. usual practice) Our specific aims are to:

Aim 1. Characterize primary care team perspectives on enhanced pain screening approaches compared with usual pain screening, including clinical usefulness and how to use skills, roles, and tasks of multidisciplinary primary care clinicians and consultants to optimize pain care. Additionally, we will try to understand Veterans' experiences with pain screening, assessment, and management (including use of opioid analgesics) in order to better link their actual experience with provider assessment and management practices. Interviews and focus groups will inform refinement of the items and screening interface; we will evaluate the interface including the PEG and 'NRS now' and the control arm for usability including among disabled veterans and for use in primary care.

Aim 2. Evaluate in a three-arm RCT the effects of enhanced pain screening approaches using a tablet and comparing the PEG, the 'NRS pain now', and usual clinician-assessed pain screening.

Hypothesis 2a: One of three enhanced pain screening approaches using the PEG, but not the 'NRS now' will be associated with improved detection of pain related disability **Hypothesis 2b:** Enhanced pain screening approaches vs. usual pain assessment will be associated with equally low missingness, Veterans, providers, and clinic and facility staff will characterize their experience with the enhanced screening protocol and important barriers, facilitators, and practical steps to inform implementation

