The 1 page field log will contain both identifiable (i.e., Full Name, last 4 digits of SSN, and contact information as needed for participation in follow up interviews) and unidentifiable data (i.e., participation status, participant ID, and observable demographics when necessary, and other research pertinent information). While in the clinic field logs will be kept on person by research staff and in a locking carrying case or secured mail bag to be transferred to a designated office. The paper documents will be stored in a locked filing cabinet inside of a locked office on VA campuses at the designated VA sites (i.e., Palo Alto, Minneapolis, Portland). A designated research assistant from each site will input the data into an encrypted and password protected Excel sheet that is kept on a secured server at VA Palo Alto. The designated research assistants at VA Portland VA Minneapolis will only have access to the cross-walk Excel sheet for their specific site. Research assistants from Palo Alto (i.e., [name] and [name]) will have access to a site specific Palo Alto Excel sheet and a master cross-walk Excel sheet that is populated by site specific crosswalks. Drs. [name] and [name] will have view only access to the master cross-walk excel sheet. At a later stage in the study, a designated programmer will have view only access to the master cross-walk excel sheet in order to compile data from both tablet survey data and medical records.

5. Tablet based survey content:

We will focus on content that is not available in existing VA administrative database the survey will include (not in this order):

- 1) an **introductory screen** which allow for registration using the unique participant number, and
- 2) **an algorithm corresponding to the three intervention arms of the RCT** and an underlying randomization engine to allocate Veterans to the three arms using a random number generator, with the corresponding pain screening measures (PEG, NRS one week, and DVPRS), and
- 3) The **Graded Chronic Pain Scale** (the gold standard for comparison),and
- 4) **Self-assessed level of physical activity**, and
- 5) **expectations and unmet need for pain treatment and management**, and

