If possible, research staff will attend a local clinic staff meeting to briefly inform the staff of the study. By partnering with local clinic leadership, we plan to send emailed invitations to eligible staff members. A log of all contact attempts will be maintained and after a maximum of 3 contact attempts the staff member will be removed from the contact list.

2. Consent Process:

Prior to the interview, a research staff member will verbally consent the participant. We have approval for a waiver of documentation of informed consent. Date of consent and person obtaining consent will be logged on the secured Excel sheets stored on VA Palo Alto Servers.

3. Data Collection Procedures:

We will conduct up to 40 telephone interviews that will take approximately 20-30 minutes. The interviews will be audio recorded and later transcribed by a VA contracted transcription service. For interview questions/content please see the Provider Interview Protocol.

4. Data Security:

Any information linking identifiable information with an assigned participant ID will be located on the secured Excel sheets. These Excel sheets will be secured and stored as previously mentioned under Phase 2: a: Data Security.

Audio files will be uploaded to the secured server located at VA Palo Alto. The audio Files will be saved using the assigned participant id. Audio files and de-identified transcripts will be transferred between VA servers and the transcriptions service via an approved secured FTP server.

Figure 1: Estimated enrollment scheme for ESP

Due to randomization the proposed enrollment algorithm will allow analytic comparison of each assessment measure / mode to the other. The table below specifies the Arm to Arm comparisons but the outcomes of each comparison are ‘clinically significant pain’ defined as pain that is moderate to severe, pain that is associated with disability, or unmet need for additional management.

Main comparison (s) of interest		Arm (s)	Comment
1	Tablet: PEG vs. NRS 1 week vs. DVPRS	1 to 2 to 3 tablet comparison	Baseline arm to arm difference

Table 1: Main analytic comparisons by screening measure and mode for outcomes of detection of pain, detection of moderate / severe pain (clinically relevant), pain associated with disability and unmet needs for treatment

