5.3 Study Evaluations/Data Analysis

Phase	Data Type	Source	Outcome	Analyses	Comment
1	Qualitative	Multidisciplinary providers, clinic staff, and Veterans	n/a	Grounded theory	Characterize screening information use in care
			management		
1	Quantitative	Patient	Pain-related disability, detection	By intervention arm*	At screening encounter

1&2	Quantitative	Patient, linked to VA health data for Veteran demographics and clinical factors	Pain missingness,	By intervention arm*	At screening encounter
2	Qualitative	Provider, patient	Satisfaction and experiences with screening including implementation	Grounded theory	Characterize experiences with the tablet and enhanced pain screening approaches

Outcome	Measure	Analysis	Model
Immediate pain related disability	NHIS pain-related disability	Arm 1,2,3 pairwise	Linear regression, adjusted for patient factors
Immediate pain missingness	NRS (nurse), NRS (tablet), PEG (tablet);	% missing pain ratings (Arm 1,2,3)	Logistic regression, adjusted for patient, rater (tablet perception), and environmental factors

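### The protocol defines the three randomised arms in conflicting ways, and the randomisation engine has no tablet 'NRS now' arm, so Hypothesis 2a and the tablet-versus-nurse comparison cannot be tested as written

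*Protocol*

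**What the plan says.** The protocol describes the arms of the Phase 2 trial in several places.

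- **Abstract, Aim 2.** Arm 1 is the PEG, and the rest reads "NRS pain now (Arm 2), compared with DVPRS (Arm 3) followed by usual clinician-assessed pain screening".
- **Section 3.0, narrative.** The first arm uses the PEG. The second repeats the NRS now on the tablet, "allowing a direct comparison of patient-administered assessment vs. clinician assessed pain and a third arm will test the NRS at one week". The same paragraph says that every subject also receives the nurse's fifth vital sign screen, "allowing a three arm comparison of each of two computer based approaches vs. usual practice".
- **Section 3.0, Aim 2.** The trial is described as "comparing the PEG, the 'NRS pain now', and usual clinician-assessed pain screening".
- **Section 5.1, Phase 2, A.5 (Tablet based survey content).** The randomisation engine allocates Veterans to three arms "with the corresponding pain screening measures (PEG, NRS one week, and DVPRS".
- **Section 5.1, Table 1.** The only main comparison is "Tablet: PEG vs. NRS 1 week vs. DVPRS".
- **Section 5.3, missingness row.** The measures are "NRS (nurse), NRS (tablet), PEG (tablet", analysed over arms 1, 2 and 3.

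Hypothesis 2a (section 3.0) predicts that the PEG, but not the NRS now, will improve detection of pain-related disability, and it speaks of both as enhanced approaches. Section 5.1 takes the nurse's NRS now rating from the vital signs record and calls it a usual care arm.

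**The concern.** The instrument each patient is randomised to is the intervention in this trial. Here the engine and the main comparison table leave out the one instrument that a named hypothesis and a stated purpose of the design depend on.

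Hypothesis 2a needs patients who answered the NRS now on the tablet. So does the mode question, whether patients report pain differently to a tablet than to a nurse: it needs the same item with the same recall window, given both ways. Section 3.0 says that the NRS now arm serves this purpose, and the Abstract lists a direct comparison of patient-reported with clinician-documented pain under the study's significance.

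If the tablet offers only a one-week NRS, no later analysis can recover an item that was never administered. If it does offer the NRS now, the planned main comparison describes a trial that was not run.

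**Working it through.** The plan gives no sample-size or power figure that bears on this point. The check is a side-by-side reading, plus one division.

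**Step 1. The arm lists.**

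| Place | PEG | Tablet NRS now | Tablet NRS one week | DVPRS | Usual nurse screening listed alongside |
|---|---|---|---|---|---|
| Abstract, Aim 2 | yes | yes | no | yes | given afterwards to all |
| 3.0 narrative | yes | yes | yes | no | given to all |
| 3.0 Aim 2 | yes | yes | no | no | yes, as third comparator |
| 5.1 engine (A.5) | yes | no | yes | yes | no |
| 5.1 Table 1 | yes | no | yes | yes | no |

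The Abstract, the 3.0 narrative and the engine with Table 1 each give a full list of three tablet arms. Any two of these lists share two instruments, but the only one common to all three is the PEG. Aim 2 in 3.0 gives a fourth set. Its third member cannot be a randomised arm, because the same section says that all subjects get the nurse screen. The 3.0 narrative also names three tablet arms and then counts two computer-based approaches. The missingness row in 5.3 lists measures rather than arms, but it omits DVPRS and gives no recall window for the tablet NRS, so it does not settle the matter.

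**Step 2. Patients who answer a tablet NRS now.** Inputs: about 650 participants in total (5.1, Recruitment and Consenting) and 1:1:1 allocation (Abstract, Methodology).

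- Under the Abstract or section 3.0: 650 / 3 = 216.7, about 217.
- Under the engine and Table 1: 0.
- At the stated ceiling of 2000 respondents: 2000 / 3 = 666.7, about 667, against 0.

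Enrolling more patients therefore does not close the gap.

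**Step 3. What follows for Hypothesis 2a.** It has two halves. The PEG half can be assessed under any of the lists, against the other tablet arms or against the nurse rating in the same patient. The half that says NRS now will not improve detection needs a tablet NRS now arm. Under the engine it has no randomised data.

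**Step 4. What follows for the mode comparison.** The nurse rating asks about pain now.

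- Tablet NRS now against nurse NRS now: mode differs, the recall window is the same.
- Tablet NRS one week against nurse NRS now: mode and recall window both differ.

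In the second contrast a difference could come from either source, and the design offers nothing to separate them.

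**Step 5. Whether another source fills the gap.** The nurse's NRS now exists for all participants, but it is the usual screen and supplies only one side of the mode comparison. Section 5.1 also has research staff ask for an NRS-now rating, but of people who decline the tablet study, who are not randomised.

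**The case against.** The strongest reply is that the loss is conditional. The engine and Table 1 agree with each other, so the operative part of the protocol is consistent, and the tablet-to-tablet comparison in Table 1 can be carried out as listed. The older-sounding text may simply not have been updated. Hypothesis 2a would also not lose everything, since its PEG half survives.

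Much of this is right. The loss of testability applies if the engine is built as section 5.1 says; if the Abstract or section 3.0 governs, the error lies in the engine text and Table 1 instead. The firm conflict is among three lists, since Aim 2 in 3.0 can be read as naming comparators and the 5.3 row as naming measures. The document also does not give the items or recall window of the DVPRS, so zero here means that no arm is designated NRS now.

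None of this removes the contradiction. Whichever text governs, another part of the protocol is wrong on what is randomised. No amendment log explains the differences, and the choice of randomised instrument is not something an analysis plan can settle afterwards. Reading the engine as correct leaves Hypothesis 2a and the direct-comparison claim standing in the current text with no arm to support them.

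**Conclusion.** The concern holds. The protocol gives conflicting sets of randomised arms, and the two operative statements leave out the tablet NRS now. Under those statements 0 of about 650 participants are randomised to it, against about 217 under the Abstract or section 3.0. Hypothesis 2a then cannot be tested as written: its PEG half stays assessable, its NRS now half does not. The tablet-versus-nurse NRS comparison is confounded with recall window. Under the other reading, Table 1 does not match the data.

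The figure of 217 assumes exactly equal allocation of 650; the contrast with zero does not depend on that number. The conclusion also assumes that the NRS now, where it is named as an arm, is a tablet item distinct from the other instruments, as section 3.0 describes it. This must be fixed, because it determines which questions the trial can answer.

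**What to change.** Establish what the tablet engine actually allocates. Then state one arm list and use it unchanged in the Abstract, section 3.0 (narrative, Aim 2 and Hypothesis 2a), the engine description, Table 1 and the 5.3 table.

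- **If the mode question and Hypothesis 2a are kept:** one arm must carry the tablet NRS now, paired within patient with the nurse's NRS now, and Table 1 should gain a row for that comparison.
- **If the arms stay PEG, NRS one week and DVPRS:** rewrite Hypothesis 2a for those instruments and delete the claim of a direct patient-versus-clinician comparison.

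In either case, describe the nurse rating as a measurement taken on all participants rather than as a usual care arm. In the 5.3 missingness row, give the recall window of the tablet NRS and list every instrument in use.

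The cost is protocol wording and a check of the tablet configuration, or a one-item change to it, with no added patients. The document does not say whether Phase 2 enrolment has begun. If it has, changing an instrument alters a randomised arm during the trial, and rewriting Hypothesis 2a changes a hypothesis after data collection started. Either change should then be dated and reported as such.

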Methodology: Clinicians, clinic staff, and facility staff will be interviewed and multidisciplinary focus groups conducted at 3 sites to characterize the range of themes related to staff perspectives on patient reported versus clinician documented pain. Development of the enhanced pain screening protocol will account for clinician perspectives informed by qualitative input, as well as subsequent patient usability testing, and then the protocol integrated into a tablet interface will be subjected to an RCT that will be placed in primary care for selected Veterans to compare with staff administered pain screening. Veterans will be randomly allocated in a 1:1:1 ratio to the three arms and analyses will evaluate a variety of quantitative and qualitative outcomes. Veteran responses to the brief tablet based pain screening protocol and additional tablet based items will be linked to Veterans’ health data to evaluate feasibility and the association with social and clinical vulnerability (e.g., perhaps minority or cognitively impaired Veterans are particularly disadvantaged by the computer vs. in person pain assessments?). Linking to existing health data allows us to minimize the length and intrusiveness of the tablet based survey, while still assessing how social and clinical vulnerability is associated with screening measure and mode. Experience during the trial will inform implementation and be gathered through interviews with both patients and providers and clinic staff.

Results: This is a new project and results have not yet been obtained.

Significance: We will characterize how to best conduct pain screening including a direct comparison of patient reported to clinician documented pain, and selection of an optimal measure to improve clinician and patient centeredness of pain measurement (e.g., by considering the incorporation of function). This project will inform national VA implementation of a preferred measure and method.

Protocol Title: Effective Screening for Pain Protocol.....	3
1.0 Study Personnel.....	4
2.0 Introduction.....	7
3.0 Objectives.....	9
4.0 Resources and Personnel.....	10
5.0 Study Procedures.....	11
5.1 Study Design.....	11
Phase 1 Overview	11
Phase 1 procedures.....	11
a. Assess the usability of patient-self-administered pain assessment via tablet.....	13
Phase 2 Overview	14
A. Multisite RCT to test pain screening approaches via tablet:.....	14
1. Recruitment and Consenting.....	14
a. Participant Eligibility.....	14

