Informatics offers an important focus in how to link screening to management. (12) Informatics leverages the electronic availability of the '5th Vital Sign' embodied in VA data systems. Although they have not been standardized or distributed in VA practices, informatics features of the VA-based trial on which the VA's national pain policy of 'stepped pain management' is based included treatment recommendations communicated through electronic alerts and email, 'order sets' based on treatment recommendations, and triggered consultations. (12,13) No specific research illuminates informatics design for pain management although features of effective alerts, clinical reminders, order support, and analogous applications are well described. (14-16) The ESP project will conduct preliminary work to characterize informatics solutions to link screening to management that can be experimentally evaluated in a subsequent study. The ESP project aims to conduct a naturalistic experiment of the use of pain screening and context that as closely as possible replicates daily VA primary care practice. The project aims to have minimal drop out because it will directly inform national implementation of a new routine pain screening process (a process that is used in approximately 30 million + health encounters annually). Representing the general population of veterans is particularly crucial for those Veterans who because of vulnerability might be both more likely to decline to participate, but are also those whose reports of pain might be most jeopardized by a move to computer based screening. (such as those with mental health conditions). The project is focused on implementation or how to roll out tablets without special research support; thus a broad variety of clinical and non-clinical staff will provide important input on how to make rollout of the tablets successful.

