informational session. The study will be described, informational sheets distributed, and staff questions will be answered regarding the study. At that time signup sheets will be placed in the primary care clinic staff break rooms for participation in the focus groups. To maintain privacy of those that want to participate we will make it known that an email will follow the in person sign up sheet if they would prefer to sign up in private. After the staff meetings, department emails will also be sent out including the study information sheet and we will provide our contact information for providers to contact us with their interest in participating in a one-on-one interview instead. We will recruit two subgroups for qualitative evaluation—primary care providers (physicians, advanced practice nurses, and physician assistants) and primary care staff (nurses, social workers, medical assistants, clerks). Primary care providers and staff in any of the three sites (GLA, Minneapolis, Portland) will be eligible to participate. If participants are uncomfortable participating in a focus group, the private interview option will be best. Of course, potential participants can opt out at any time. At the beginning of each one-on-one interview as well as the start of the focus groups, verbal consent will be obtained for participation. . First research staff will distribute information sheets and go over the information provided in the sheet, then a question and answer time will follow. After all questions are resolved, participants will be verbally consented and this will be audio recorded. We will make sure participants understand this is research, the purpose, they will be recorded and they can refuse to answer any questions as well as contact us if needed. Providers' signup on the signup sheets for participation in the focus group will be a sign of interest in participation.

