We will conduct up to 40 telephone interviews that will take approximately 25-45 minutes. The interviews will be audio recorded and later transcribed by a VA contracted transcription service. For interview questions/content please see the Patient Interview Protocol.

4. Compensation:

After completion of the telephone interview, research staff will mail a \$30 gift card to the Veteran's preferred mailing address. There will be no indication of their participation in the study sent with the gift card. Veterans may also have the option of picking the gift card up in person if local research staff is able to safely accommodate.

5. Data Security:

Any information linking identifiable information with the assigned participant ID will be located on the Field Log and/or the secured Excel sheets. These documents will be secured and stored as previously mentioned under Phase 2: a: Data Security.

Audio files will be uploaded to the secured server located at VA Palo Alto. The audio Files will be saved using the assigned participant id. Audio files and de-identified transcripts will be transferred between VA servers and the transcriptions service via an approved secured FTP server.

C. Provider interviews:

In order to identify barriers and facilitators to implementation of the tablet based pain screening we will conduct telephone or in-person interviews with up to 40 VA providers and clinical staff. This information will help guide future refinements to the tablet screening approach and provide valuable feedback for development of future interventions to improve integrated pain screening and management.

1. Recruitment and Consenting:

If possible, research staff will attend a local clinic staff meeting to briefly inform the staff of the study. By partnering with local clinic leadership, we hope to be able to send emailed invitations to appropriate staff members. Following this email invitation, we will contact the providers by telephone to either complete the verbal consent process and interview or to schedule a later time to complete the verbal consent process and interview. A log of contact attempts will be maintained, and after a maximum of 3 contact attempts the staff member will be removed from the contact list.

a. Participant Eligibility:

VA Clinic staff may be eligible to participate in the interview if they are licensed medical staff within a clinic that is already included in this study.

b. Recruitment:

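### The Phase 2 staff-interview eligibility rule is narrower than the informants named in the Abstract's Aim 2 and Hypothesis 2b, so the staff-experience part of 2b can be only partly answered

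*Protocol*

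**What the plan says.** **What is promised.** Aim 2 in the Abstract includes "interviews with patients, clinic, and facility staff" among its sources. Hypothesis 2b (section 3.0) states that "Veterans, providers, and clinic and facility staff will characterize their experience with the enhanced screening protocol", together with barriers, facilitators and practical steps for implementation. The Methodology part of the Abstract says that experience during the trial will be "gathered through interviews with both patients and providers and clinic staff". The Introduction adds that "a broad variety of clinical and non-clinical staff will provide important input on how to make rollout of the tablets successful".

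**What is arranged.** Section 5.1, Phase 2, part C (Provider interviews) is the only Phase 2 component that recruits staff. Its purpose is given as "In order to identify barriers and facilitators to implementation of the tablet based pain screening", and it plans "interviews with up to 40 VA providers and clinical staff". Under Participant Eligibility, staff may be eligible "if they are licensed medical staff within a clinic that is already included in this study". No other criterion is given, and the emailed invitations go to eligible staff. The table in section 5.3 lists the Phase 2 qualitative source as provider and patient.

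**How the protocol uses the word staff.** In the Phase 1 recruitment text, one of the two subgroups is "primary care staff (nurses, social workers, medical assistants, clerks", set apart from a subgroup of primary care providers.

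**The concern.** The aims name one set of informants and the procedure recruits a smaller one. Hypothesis 2b lists providers separately from clinic and facility staff, so the terms are not interchangeable, and the Phase 1 text makes the same separation. A site applying the eligibility sentence literally would turn away a clerk for want of a licence. It would turn away a facility-level informant for not belonging to a participating clinic.

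At stake is the implementation element of 2b. The protocol says it is meant to inform wider VA use of tablet screening, run without research support. A report on staff experience drawn only from licensed clinic staff would either leave the named groups out or appear to speak for people who were never eligible.

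**Working it through.** No arithmetic applies; the check is a comparison of the texts.

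**Step 1: who is named, and who can be interviewed after the tablet is in use.**

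| Informant group | Named in Abstract Aim 2 or Hypothesis 2b | Phase 2 route |
|---|---|---|
| Veterans | Both | Open: patient follow-up interviews, up to 40 |
| Providers | Hypothesis 2b | Open: provider interviews |
| Licensed clinic staff, such as licensed nurses | Both, as clinic staff | Open: same component |
| Clerks | Both, as clinic staff in the Phase 1 usage | Closed by the licence condition |
| Medical assistants | Both, as clinic staff in the Phase 1 usage | Undetermined: the protocol does not say whether they are licensed |
| Facility staff outside participating clinics | Both, as facility staff | Closed by the clinic condition |

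**Step 2: is there another Phase 2 route?** The run-in period in section 5.1 is for evaluating and refining implementation, but it names no staff informants. The informal observation and questions during the RCT concern patients using the tablet. The section 5.3 table adds no further source. No other route is described.

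**Step 3: can Phase 1 supply the missing experience?** The Phase 1 focus groups do admit clerks, phone screeners and medical assistants. They take place before the tablet is deployed, because their findings are meant to shape it. They can give views on a planned approach, but not experience with the one in use, which is what 2b describes. Phase 1 also recruits staff at GLA, Minneapolis and Portland, whereas the Phase 2 procedures name Palo Alto, Minneapolis and Portland, so Palo Alto clinic staff are not in the Phase 1 pool at all.

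**Step 4: is part C consistent within itself?** Its opening sentence speaks of providers and clinical staff; its eligibility sentence requires a licence. If any clinical staff are unlicensed, the two sentences already differ.

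**Result.** Of the up to 40 staff interviews, none is open to clerks or to facility staff outside participating clinics. Three of the six groups in the table have a clear route, two have none, and one depends on a fact that the protocol does not give.

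**The case against.** Several points on the other side are sound, and they limit what can be claimed.

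- **A reader might infer that Aim 2 and 2b promise clerical or non-clinical staff by name.** They do not. They say clinic and facility staff. Non-clinical staff appear in the Introduction, clerks in the Phase 1 text, and Aim 2 as restated in section 3.0 mentions no staff interviews. Clerks come in only through the protocol's own description of primary care staff.
- **A reader might infer that the rule prevents 2b from being answered.** It does not. Patients, providers and licensed clinic staff are covered. Only facility staff outside the participating clinics are a named group left wholly unserved.
- **A reader might take the Introduction's sentence as contradicted.** That is weak. The sentence asks for input on rollout without saying when, and Phase 1 partly provides it, with the placing and supervision of tablets as its own example.
- **A reader might infer that barriers at check-in will be missed.** The documents do not establish this. Research staff approach Veterans after check-in, log in, hand over the tablet and oversee its use; clerks are given no task in operating it.
- **The eligibility sentence is permissive in form and may be loose drafting.** That is fair. It is nevertheless the only criterion under its heading, and sites would apply it as a restriction.
- **The component is descriptive.** True: randomization, the arm comparisons, the sample size and the quantitative outcomes are untouched.

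What remains is the mismatch between the stated informants and the eligibility rule, together with the matching entry in section 5.3. Phase 1 does not remove it.

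**Conclusion.** The concern holds in limited form. The eligibility rule in section 5.1, part C, and the Phase 2 source entry in section 5.3 are narrower than the informants named in the Abstract's Aim 2 and Hypothesis 2b. The staff-experience element of 2b is therefore only partly answerable. The effect is confined to that qualitative element.

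The conclusion assumes that the single eligibility sentence is applied as a restriction, that clerks are not licensed medical staff, and that no recruitment route exists outside the text shown. The Provider Interview Protocol to which part C refers is not in the document. The status of medical assistants stays open. The conclusion about facility staff outside the participating clinics does not depend on licensure.

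**What to change.** Widen the eligibility sentence in section 5.1, Phase 2, part C, to cover providers, clinic staff whether licensed or not, and facility staff who work in or support a participating clinic. Keep the present maximum of 40 interviews. Change the Phase 2 qualitative source in section 5.3 to match. No quota by staff group is needed; nothing in the protocol calls for one.

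If the sponsor intends licensed staff only, narrow the wording of the Abstract's Aim 2 and Hypothesis 2b instead. Either route removes the conflict, but only the first lets the trial report on the groups now named.

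The cost is one sentence and one table entry, with somewhat fewer interviews left for licensed staff. The sponsor should check that the waiver of documentation of consent, which section 5.2 describes for provider interviews, and the interview guide also suit the wider group. The document does not settle either point.
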